1. INTRODUCTION

1.1. Background and rationale

Most, if not all, patients receiving pelvic radiotherapy will develop permanently changed bowel habits as a result of radiation exposure to the bowels [1,2]. As the tissue is exposed to ionizing radiation an acute inflammation is triggered, followed by a low-grade inflammation, ischemia and fibrosis [3]. The acute symptoms will subside, but others may persist and new ones develop years to decades after the cancer treatment, severely affecting quality of life [4]. Five symptom clusters (syndromes) can be distinguished years after pelvic radiotherapy [5]. The symptoms are related to a continuous urgent need to defecate (fecal-urgency syndrome), fecal leakage (fecal-leakage syndrome), leakage of mucus (excessive mucus discharge), uncontrollable flatulence (excessive gas discharge) and anal bleeding (blood discharge) [5]. The fecal-urgency syndrome is one of the most common and problematic syndromes among cancer survivors after radiotherapy [6]. There is limited data to establish the underlying mechanisms for the five syndromes and there is a lack of efficient preventative strategies and treatments [7].

A handful of studies in human and animals suggests that dietary interventions may affect both acute and chronic symptoms, but the evidence is weak [8]. Today, there are no established, evidence-based, dietary recommendations for patients undergoing pelvic radiotherapy or pelvic cancer survivors [9]. Wedlake *et al.* provided some support that a high-fiber diet (16 g non-starch polysaccharides/day) may improve intestinal health one year after pelvic radiotherapy [10]. Dietary fiber, primarily found in whole grain products, vegetables, and fruit, may prevent radiation-induced injury of the intestinal wall. This is likely to be, at least in part, due to the production of short chain fatty acids that are used as an energy source by the colonocytes and contribute to an improved intestinal integrity [11,12]. Nonetheless, both in Sweden and internationally, many patients are advised to reduce intake of dietary fiber during pelvic radiotherapy [10,13]. This advice probably stems from the notion that fiber intake might cause bloating and increased discomfort, and thereby exacerbate the acute symptoms. In FIDURA (dietary Fiber Intake DUring Radiotherapy) a randomized, placebo-controlled, double-blinded clinical trial, we collect data to develop evidence-based nutritional recommendations with regards to dietary fiber intake for patients undergoing pelvic radiotherapy and irradiated pelvic cancer survivors.

1.2. Objectives

1.2.1. Primary Objectives

There are two co-primary objectives:

Primary Objective 1: Investigate if the addition of 6 g psyllium husk, compared to placebo, will reduce the level of C-reactive protein (CRP) measured four weeks after the end of radiotherapy.

Primary objective 2: Investigate if the addition of 6 g psyllium husk, compared to placebo, will reduce the level of Urgency Syndrome measured one year after the end of radiotherapy.

1.2.2. Secondary Objectives

Secondary Objective 1: Investigate if the addition of 6 g psyllium husk, compared to placebo, will affect the level of Leakage Syndrome, measured one year after the end of radiotherapy

Secondary Objective 2: Investigate if the addition of 6 g psyllium husk, compared to placebo, will affect the level of Excessive Gas Discharge Syndrome, measured one year after the end of radiotherapy

Secondary Objective 3: Investigate if the addition of 6 g psyllium husk, compared to placebo, will affect the level of Excessive Mucus Discharge Syndrome, measured one year after the end of radiotherapy

Secondary Objective 4: Investigate if the addition of 6 g psyllium husk, compared to placebo, will affect the level of Blood Discharge Syndrome, measured one year after the end of radiotherapy

2. STUDY METHODS

2.1. Trial design

In this triple-blind, superiority, parallel study, participants were automatically randomized to one of two groups through a study-specific database. Participants received blinded capsules containing either psyllium husk or placebo, and all participants were given individualized dietary advice e.g., to daily eat at least 16 g of dietary fiber (Figure 1). During the study, the participants filled out three questionnaires at a digital application and donated four blood samples and five fecal samples (Figure 1). Repeated telephone follow-ups were made to ensure that the participants did not experience aggravated symptoms owing to study intervention.

Patients with gynecological cancer and prostate cancer scheduled for curative pelvic radiotherapy were recruited from the oncology clinic, urology clinic, or gynecological clinic at Sahlgrenska University Hospital in Gothenburg or Skåne University Hospital in Malmö and Lund.

[figure not shown]

Figure 1. The study design of FIDURA (dietary Fiber intake DUring pelvic RAdiotherapy)

The two groups received the same information but were provided with different capsules. The active capsules include a fiber supplement (Finax® psyllium husk) which is rich in gel-forming soluble fiber, whilst the matched placebo (maltodextrin) does not include any fiber. The participants were instructed to consume 15 capsules per day (which include 6 g of psyllium husk, equal to 5g dietary fiber). Instructions were given how to ingest the capsules (enough fluid intake, mix with drinks or foods, and avoid ingest together with drugs) and gradually step up the intake during seven days.

2.2. Randomization

Simple randomization was used to allocate participants 1:1 to either placebo or fiber capsules.

2.3. Power

The original planned sample size was 500 patients, with 250 in each randomized arm. Trial recruitment was stopped when the PI sadly died in July 2023. At that point a total of 354 patients had been recruited (190 randomized to one arm and 164 to the other arm). The original sample size calculation is shown below.

In order to estimate the power of the Mann-Whitney to detect the relative effect of the two fiber regimes a simulation study was undertaken, modeling the potential effect as a shift in the empirical distribution of the factors scores, interpreted as syndrome intensities, associated with the Urgency Syndrome among gynecological cancer survivors. A selection of the range of theoretically relevant shifts was studied at 101 equidistant locations, including the zero shift. At each such point 1000 samples of sizes 250 were drawn with replacement from the original and shifted distributions, and a Mann-Whitney test was performed and evaluated at the 0.05 level. Once again at each such point the fraction of such tests suggesting

a rejection of the null hypothesis was recorded. These fractions were finally used as the basis of the loess smoothed function found in Figure 2. An investigation of the function suggested that a power of 80 % is attained at a shift of 1.06.

[figure not shown]

Figure 2. Simulated power function with respect to location shift.

The study was stopped earlier, therefore a power calculation was performed on the final dataset:

Power calculation: For both primary outcomes, we have recalculated the power based on an assumed dropout rate of 10% at 4 weeks after radiotherapy and 15% dropout rate at the one-year follow-up. Hence the power is based on sample sizes of 318 for CRP at 4 weeks and 300 for Urgency Syndrome at 12 months. We have used an alpha of 0.05 for both comparisons. For CRP at 4 weeks, following the results reported in Pal et al [14] we assume that in the control group CRP will increase by 400ng/mL, and that in the intervention group it will decrease by 700ng/mL, with a common SD of 3100. With these assumptions, we will have 88% to detect a difference. For Urgency Syndrome at 12 months, based on results we published in 2019 [15] we assume that at baseline the mean syndrome score will be -2.1 (SD=2.8) in both arms, but will increase during the study to 1.1 (SD=4.6) among the control group. Assuming that the intervention mitigates half of this increase, we estimate that in the intervention group, the mean urgency syndrome score will increase to -0.5 (SD=4.6). Hence the change in the two groups will be 3.2 and 1.6, respectively, with a common SD of 3.6. Under these assumptions, we will have 97% power to detect a difference.

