2.4. Framework

This is a superiority trial, with the aim of showing that the addition of dietary fiber will improve patient symptoms, compared to the control group.

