3. STATISTICAL PRINCIPLES

3.1. Confidence intervals and p-values

95% confidence intervals will be applied and P values <0.05 will be considered statistically significant.

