5. ANALYSIS

5.1. Outcome definitions

5.1.1. Co-Primary outcomes

The co-primary outcome of change in concentration of hypersensitive CRP will be calculated as

$$\text{CRP at four weeks after the end of radiotherapy} - \text{CRP at baseline}$$

Hence, a positive value for the change will indicate an increase in CRP and a negative value will indicate a decrease.

The co-primary outcome of change in urgency syndrome will be calculated as

Urgency Syndrome at one-year after the end of radiotherapy – Urgency Syndrome at baseline

Higher scores of the Urgency Syndrome indicate worse symptoms. Hence a negative value for the change in Urgency score will indicate a worsening of symptoms over the duration of the trial, and a positive value will indicate an improvement in symptoms.

The Urgency Syndrome Score for each participant at each timepoint will be calculated using the factor loadings identified in Steineck et al [5].

All questions related to the urgency factor loadings in the paper by Steineck et al [5] are included in Fidura except one: 'Immediate need to defecate'. The reason is because it was very similar to the variable 'Sudden defecation urgency requiring lavatory'. The new question is on the same scale (1-7) as the old question, and we took the decision to substitute it without further amendments.

The urgency syndrome score for each participant and occasion is based on 14 questions, each of which is scored on a 1-7 scale, where 1 indicates the lowest level of symptoms and 7 the highest.

To calculate the score, first, for each participant and occasion, the variable will be standardized using the formula $X - \mu / \sigma$, where:

- X is the score for that participant for that specific question
- μ is the mean of that specific question from all participants (both arms) at the specific timepoint (baseline or follow-up)
- σ is the standard deviation of all responses (both arms) to that question at that timepoint

Then, each question will be multiplied by a loading factor. Finally, the scores will be summed up to a final score.

| Q # | Question text (translated from Swedish) | Loading factor |
|-----|---|----------------|
| 46 | Loose stools the last 3 months at baseline /the last week, 4 weeks after radiotherapy /the last three months, one-year after radiotherapy | 0.71 |

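### The SAP tests two co-primary outcomes at the full 0.05 each but never says whether one or both must succeed

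*SAP*

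**What the plan says.** Section 1.2.1 opens with "There are two co-primary objectives": that psyllium lowers CRP four weeks after radiotherapy, and that it lowers the Urgency Syndrome score one year after. Section 2.3 recalculates power for each outcome separately and says "We have used an alpha of 0.05 for both comparisons". It reports 88% for CRP and 97% for urgency, and no power for succeeding on both.

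Section 3.1 gives the only significance rule in the document: "95% confidence intervals will be applied and P values <0.05 will be considered statistically significant". Section 5.2 gives each outcome its own linear regression. Section 2.4 gives the overall aim: "This is a superiority trial, with the aim of showing that the addition of dietary fiber will improve patient symptoms, compared to the control group".

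None of these sections, nor 5.1.1 or 5.3, defines co-primary, requires both outcomes, orders the two tests or divides the 0.05.

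**The concern.** With two primary tests, the error rate of the primary conclusion depends on how the two results are combined. Where both must be significant, each can be tested at 0.05 without adjustment. Where either is enough, testing both at 0.05 gives an overall error well above 5%. The SAP fits both rules and states neither.

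This matters most when the results are mixed. Suppose one p-value is 0.03 and the other 0.20. Under one rule the trial is positive and under the other it is negative, on the same data. If the rule is not fixed in advance, it can be chosen after the results are known. The multiplicity rule belongs in an SAP, and section 3.1 is where this one sets its significance criterion, so the gap is in the document at hand.

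**Working it through.** **Inputs, all from SAP section 2.3.** 354 recruited; dropout 10% at four weeks and 15% at one year; CRP change +400 against −700 ng/mL (difference 1100), SD 3100; urgency change 3.2 against 1.6 (difference 1.6), SD 3.6; alpha 0.05 for each. The SAP gives no correlation between the two tests, so every correlation below is an assumption.

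**1. The plan's own figures.** 354 × 0.90 = 318.6 and 354 × 0.85 = 300.9, matching the stated 318 and 300. For a two-sample t-test with equal arms, the non-centrality is difference / (SD × √(4/N)).
- CRP: 1100 / (3100 × √(4/318)) = 3.16. Power at two-sided 0.05 is 88.4%.
- Urgency: 1.6 / (3.6 × √(4/300)) = 3.85. Power at two-sided 0.05 is 97.0%.

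Both stated powers are reproduced, with the whole two-sided 0.05 spent on each outcome. At two-sided 0.025 the powers are 81.9% and 94.4%. Using the 190:164 allocation instead of equal arms changes CRP only slightly, to 88.2% and 81.6%.

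**2. Either outcome suffices, both nulls true.** Independent tests: 1 − (1 − 0.05)² = 9.75%. With bivariate normal test statistics:

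| Assumed correlation | At least one false positive |
|---|---|
| 0 | 9.75% |
| 0.3 | 9.5% |
| 0.5 | 9.1% |
| 0.9 | 7.0% |

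The ceiling is 0.05 + 0.05 = 10%. Counting only false claims of benefit, since both objectives are directional, the independent figure is 1 − (1 − 0.025)² = 4.94%, against 2.5% for a single two-sided 0.05 test. The near-doubling is the same.

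**3. Both outcomes required.** A false claim needs at least one true null to be rejected at 0.05, so the error is at most 5% whatever the correlation. On the SAP's assumptions, joint power with independent tests is 0.8838 × 0.9697 = 85.7%. It cannot exceed the smaller of the two powers, 88.4%.

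**4. Holm at overall two-sided 0.05.** With both nulls true and independent tests, the error is 1 − (1 − 0.025)² = 4.94%. For benefit claims only:
- Exactly one rejection has probability 2 × 0.025 × 0.95 = 0.0475.
- Two rejections have probability 0.05² − 0.025² = 0.001875.
- A false claim of benefit therefore has probability 0.5 × 0.0475 + 0.75 × 0.001875 = 0.0252.

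CRP is declared significant if its p-value is below 0.025, or if it is below 0.05 and the urgency p-value is below 0.025. With independent tests and p the urgency power at 0.025, CRP power is 0.8185 + (0.8838 − 0.8185) × p.
- Worst case, p = 0: 81.9%, a loss of 6.5 points.
- SAP's urgency assumptions, p = 0.944: 88.0%, a loss of about 0.4 points.

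**5. How often the missing rule would decide the result.** If both planned effects hold and the tests are independent, the chance that exactly one is significant is 0.8838 × (1 − 0.9697) + 0.9697 × (1 − 0.8838) = 0.027 + 0.113 = about 14%.

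**The case against.** The best defence is that co-primary, with alpha left unsplit, is a common way of saying that both must succeed. If that is meant, 0.05 each is correct and no error is inflated. This stands as a possible reading, and it rules out treating 9.75% as an established property of the plan. It is not what the SAP says, though. The term is undefined, the objectives are two separate questions, and a both-required design would be expected to report a joint power, which is absent.

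A second defence is that the two questions are distinct, a biomarker at four weeks and a symptom score at one year, and could be answered separately with no overall claim. Each test then keeps its own 5% error. Whether that needs adjustment is partly a matter of judgement, but this intention is not stated either. Section 2.4 frames the aim as improving symptoms, and CRP is not a symptom, so a success on CRP alone would sit awkwardly with that aim. That is a hint against an either-outcome rule, but it does not replace a stated one.

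A reader might infer the stronger charge that this SAP runs its primary analysis at about 10% error. The document does not support that: it neither grants nor excludes a claim resting on one outcome. Nor is either individual test invalid at 0.05.

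**Conclusion.** The decision rule across the two co-primary outcomes is missing and should be fixed before analysis. The consequence is conditional. If either outcome suffices, the overall false-positive rate is 9.75% with independent tests and about 9.1% at an assumed correlation of 0.5. If both are required, it is at most 5%, and the figure to report is a joint power of about 86% (independent tests, SAP's assumptions), never above 88%.

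The error rates do not depend on the SAP's effect sizes. The joint power and the 88% CRP power under Holm do, because they use the urgency assumptions in section 2.3. Those put the baseline mean at −2.1, which does not fit the within-timepoint standardisation in section 5.1.1. That is a separate issue to be raised on its own, and the multiplicity point does not rest on it.

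**What to change.** Add one rule to section 3.1 before the data are analysed. The choice is the sponsor's:

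- **Either outcome may support a claim.** State that the two co-primary hypotheses are tested by Holm's procedure at an overall two-sided 0.05: the smaller p-value against 0.025 and, only if that is significant, the other against 0.05.
- **Both are required.** State that both co-primary outcomes must be significant at two-sided 0.05.

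Then align section 2.3. Under Holm, give CRP power as about 82% at worst and about 88% on the SAP's assumptions with independent tests. Under both-required, give joint power as about 86% if independent, with 88% as the ceiling.

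The change is to wording only; no data collection is affected. Holm costs CRP at most 6.5 points of power, and about 0.4 points if both planned effects hold and the tests are independent. Both-required costs no alpha, but the power to report is lower than either figure now shown.

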2.4. Framework

This is a superiority trial, with the aim of showing that the addition of dietary fiber will improve patient symptoms, compared to the control group.

2.5. Statistical interim analysis and stopping guidance

No interim analysis was planned nor performed. The trial stopped recruitment early following the death of the principal investigator. At that point 354 people had been randomized. Follow up visits are ongoing, final visit will take place in August 2024.

2.6. Timing of final analysis

When all participants have finished their one-year follow-up.

2.7. Timing of outcome assessment

Baseline data on CRP levels and urgency syndromes were collected two weeks prior to the start of radiotherapy, with outcome data gathered at multiple time points: immediately before, during, four weeks, and one year after treatment. The collection of data is presented in Figure 1. The primary CRP endpoint is measured at four weeks after radiotherapy. The primary urgency endpoint is measured one year after radiotherapy.

3. STATISTICAL PRINCIPLES

3.1. Confidence intervals and p-values

95% confidence intervals will be applied and P values <0.05 will be considered statistically significant.

3.2. Adherence and Protocol deviations

We will report the proportion of capsules consumed by each participant less than/more than 80 percent of capsule intervention. Adherence will be measured by capsules given subtracted by capsules returned.

| | Control arm (N=xx) | Intervention arm (N=xx) |
|-----------------------------|--------------------|-------------------------|
| Percentage consumed: | | |
| median (IQR) | | |
| <80% | n (%) | n (%) |
| ≥80% | n (%) | n (%) |

3.3. Analysis population

1. Intention-to-treat. This will consist of all randomized participants who initiated at least one task in the study, who will be analyzed according to their original assignment.
2. Per-protocol. Participants who consumed at least 80 percent of the capsules.

4. TRIAL POPULATION

4.1. Screening data

The table will be completed.

| | Included (N=xx) | Excluded (N=xx) |
|-------------------|------------------------|------------------------|
| Age: median (IQR) | xx (xx - xx) | xx (xx - xx) |
| Sex | | |
| Female | xx (xx%) | xx (xx%) |
| Male | xx (xx%) | xx (xx%) |

4.2. Eligibility

Inclusion criteria:

- Patients with gynecological cancer and prostate cancer scheduled for curative pelvic radiotherapy.

Exclusion criteria:

- preoperative stoma as determined by the treating physician to prevent participation.
- swallowing difficulties or ileus condition as determined by the treating physician to prevent participation.
- cognitive dysfunction as determined by the treating physician to prevent participation.
- need for an interpreter to communicate in Swedish.

4.3. Recruitment

We will complete a CONSORT flow diagram to show number of participants recruited and the number of (and reasons for) withdrawals.

4.4. Baseline patient characteristics

The table will be completed.

| Characteristic | Control arm (N=xx) | Intervention arm (N=(xx)) |
|-----------------------|-------------------------------|--------------------------------------|
| Sex | | |
| Female | n (%) | n (%) |
| Male | n (%) | n (%) |

| | | |
|--|--------------|--------------|
| Age; median (IQR) | xx (xx - xx) | xx (xx - xx) |
| BMI (kg / m²) | | |
| <25 | n (%) | n (%) |
| ≥ 25, < 30 | n (%) | n (%) |
| ≥ 30 | n (%) | n (%) |
| Type of cancer | | |
| Gynecological | n (%) | n (%) |
| Prostate | n (%) | n (%) |
| Cytostatic | | |
| Before/during/after radiotherapy | n (%) | n (%) |
| Before and during radiotherapy | n (%) | n (%) |
| During and after radiotherapy | n (%) | n (%) |
| Radiation fractions | | |
| Short | n (%) | n (%) |
| Long | n (%) | n (%) |
| Medicine dose | | |
| Antidiarrheal agents | n (%) | n (%) |
| Bulking agents | n (%) | n (%) |
| Gas-reducing agents | n (%) | n (%) |
| Laxative agents | n (%) | n (%) |
| Smoking | | |
| Never / stopped > 5 years ago | n (%) | n (%) |
| Smoked before RT / stopped < 5 years ago | n (%) | n (%) |
| Smoked before and during RT | n (%) | n (%) |
| Physically active | | |
| No | n (%) | n (%) |
| Yes | n (%) | n (%) |

5. ANALYSIS

5.1. Outcome definitions

5.1.1. Co-Primary outcomes

The co-primary outcome of change in concentration of hypersensitive CRP will be calculated as

$$\text{CRP at four weeks after the end of radiotherapy} - \text{CRP at baseline}$$

Hence, a positive value for the change will indicate an increase in CRP and a negative value will indicate a decrease.

The co-primary outcome of change in urgency syndrome will be calculated as

Urgency Syndrome at one-year after the end of radiotherapy – Urgency Syndrome at baseline

Higher scores of the Urgency Syndrome indicate worse symptoms. Hence a negative value for the change in Urgency score will indicate a worsening of symptoms over the duration of the trial, and a positive value will indicate an improvement in symptoms.

The Urgency Syndrome Score for each participant at each timepoint will be calculated using the factor loadings identified in Steineck et al [5].

All questions related to the urgency factor loadings in the paper by Steineck et al [5] are included in Fidura except one: 'Immediate need to defecate'. The reason is because it was very similar to the variable 'Sudden defecation urgency requiring lavatory'. The new question is on the same scale (1-7) as the old question, and we took the decision to substitute it without further amendments.

The urgency syndrome score for each participant and occasion is based on 14 questions, each of which is scored on a 1-7 scale, where 1 indicates the lowest level of symptoms and 7 the highest.

To calculate the score, first, for each participant and occasion, the variable will be standardized using the formula $X - \mu / \sigma$, where:

- X is the score for that participant for that specific question
- μ is the mean of that specific question from all participants (both arms) at the specific timepoint (baseline or follow-up)
- σ is the standard deviation of all responses (both arms) to that question at that timepoint

Then, each question will be multiplied by a loading factor. Finally, the scores will be summed up to a final score.

| Q # | Question text (translated from Swedish) | Loading factor |
|-----|---|----------------|
| 46 | Loose stools the last 3 months at baseline /the last week, 4 weeks after radiotherapy /the last three months, one-year after radiotherapy | 0.71 |
| 47 | Returned to the toilet within one hour after defecation to again empty the bowel the last 3 months at baseline /the last week, 4 weeks after radiotherapy /the last three months, one-year after radiotherapy | 0.61 |

| | | |
|----|--|------|
| 48 | Sudden bowel movements that required an immediate visit to the toilet in the last 3 months at baseline /the last week, 4 weeks after radiotherapy /the last three months, one-year after radiotherapy | 0.85 |
| 49 | Time to hold bowel movements during the last 3 months at baseline /the last week, 4 weeks after radiotherapy /the last three months, one-year after radiotherapy | 0.69 |
| 50 | Without warning leaked feces into the clothes, despite having previously emptied bowels, in the last 3 months at baseline /the last week, 4 weeks after radiotherapy /the last three months, one-year after radiotherapy | 0.35 |
| 51 | Without warning emptied all feces into the clothes in the last 3 months at baseline /the last week, 4 weeks after radiotherapy /the last three months, one-year after radiotherapy | 0.26 |
| 52 | Leakage of loose stools, while awake, in the last 3 months at baseline /the last week, 4 weeks after radiotherapy /the last three months, one-year after radiotherapy | 0.40 |
| 53 | Leakage of loose stools, while asleep, in the last 3 months at baseline /the last week, 4 weeks after radiotherapy /the last three months, one-year after radiotherapy | 0.22 |
| 57 | Felt bloated for the last 3 months at baseline /the last week, 4 weeks after radiotherapy /the last three months, one-year after radiotherapy | 0.32 |
| 58 | Not been able to hold gas (farts) in the rectum when needed in the last 3 months at baseline /the last week, 4 weeks after radiotherapy /the last three months, one-year after radiotherapy | 0.25 |
| 60 | Bad-smelling gas emissions (farts) that you have not been able to stop in the last 3 months at baseline /the last week, 4 weeks after radiotherapy /the last three months, one-year after radiotherapy | 0.27 |
| 67 | Itching in the anus during the last 3 months at baseline /the last week, 4 weeks after radiotherapy /the last three months, one-year after radiotherapy | 0.23 |
| 68 | Pain in the anus during the last 3 months at baseline /the last week, 4 weeks after radiotherapy /the last three months, one-year after radiotherapy | 0.22 |
| 69 | Abdominal pain the last 3 months at baseline /the last week, 4 weeks after radiotherapy /the last three months, one-year after radiotherapy | 0.34 |

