5.1.2. Secondary outcomes

Unless otherwise stated, all secondary outcomes will be measured as change from baseline, as described above for the primary endpoints.

Leakage Syndrome

Leakage Syndrome scores will be calculated using the same method described above for Urgency Syndrome. The questions and associated factor loadings are described below:

| Q | Question text (translated from Swedish) | Loading factor |
|----|--|----------------|
| 50 | Without warning leaked feces into the clothes, despite having previously emptied bowels, in the last 3 months at baseline /the last week, 4 weeks after radiotherapy /the last three months, one-year after radiotherapy | 0.68 |
| 51 | Without warning emptied all feces into the clothes in the last 3 months at baseline /the last week, 4 weeks after radiotherapy /the last three months, one-year after radiotherapy | 0.47 |
| 52 | Leakage of loose stools, while awake, in the last 3 months at baseline /the last week, 4 weeks after radiotherapy /the last three months, one-year after radiotherapy | 0.62 |
| 53 | Leakage of loose stools, while asleep, in the last 3 months at baseline /the last week, 4 weeks after radiotherapy /the last three months, one-year after radiotherapy | 0.53 |
| 54 | Leakage of solid stools, while awake, in the last 3 months at baseline /the last week, 4 weeks after radiotherapy /the last three months, one-year after radiotherapy | 0.43 |
| 55 | Leakage of solid stools, while asleep, in the last 3 months at baseline /the last week, 4 weeks after radiotherapy /the last three months, one-year after radiotherapy | 0.34 |
| 60 | Smelled feces the last 3 months at baseline /the last week, 4 weeks after radiotherapy /the last three months, one-year after radiotherapy | 0.52 |

Excessive Gas Discharge Syndrome

Excessive Gas Discharge Syndrome scores will be calculated using the same method described above for Urgency Syndrome. The questions and associated factor loadings are described below:

| Q | Question text (translated from Swedish) | Loading factor |
|----|---|----------------|
| 58 | Not been able to hold gas (farts) in the rectum when needed in the last 3 months at baseline /the last week, 4 weeks after radiotherapy /the last three months, one-year after radiotherapy | 0.79 |

| | | |
|----|--|------|

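### The SAP reads the sign of the co-primary urgency change backwards, so a benefit of psyllium could be reported as harm and harm as benefit

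*SAP*

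**What the plan says.** SAP 5.1.1 sets out the co-primary urgency outcome in three steps.

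- The change is "Urgency Syndrome at one-year after the end of radiotherapy – Urgency Syndrome at baseline".
- The direction of the scale is "Higher scores of the Urgency Syndrome indicate worse symptoms".
- The reading of the sign is "Hence a negative value for the change in Urgency score will indicate a worsening of symptoms over the duration of the trial", and conversely "a positive value will indicate an improvement in symptoms".

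The score is built from 14 questions, "each of which is scored on a 1-7 scale, where 1 indicates the lowest level of symptoms and 7 the highest". Each answer is standardised within its timepoint, multiplied by its loading and summed.

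Other sections also bear on direction. Primary objective 2 (1.2.1) asks whether psyllium lowers the urgency level at one year. Section 2.3 assumes that the score rises under placebo and that psyllium prevents half of the rise. Section 5.2 fits a linear regression to the change score with treatment, site and baseline score as covariates, and does not say which sign of the treatment coefficient favours psyllium. For the four secondary syndromes, 5.1.2 says: "Unless otherwise stated, all secondary outcomes will be measured as change from baseline, as described above for the primary endpoints".

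**The concern.** The third step in 5.1.1 is presented as following from the first two, but it is their reverse. If follow-up minus baseline is positive, the score has risen, and a higher score is worse.

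This sentence is the only explicit rule in the SAP for reading the sign of the urgency change. The trial is a superiority trial (2.4), and its conclusion on this endpoint depends on the direction of one regression coefficient. An analyst or author who applies the sentence literally would report a beneficial coefficient as harm and a harmful one as benefit.

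The secondary syndromes have less protection. Their objectives in 1.2.2 ask only whether psyllium affects each score, without naming the direction that counts as benefit, so a reader has less to check the rule against.

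**Working it through.** **Inputs**

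| Quantity | Value | Source |
|---|---|---|
| Change | one-year score − baseline score | SAP 5.1.1 |
| Scale | higher = worse; items 1 (lowest symptoms) to 7 (highest) | SAP 5.1.1 |
| Urgency loadings | 14, all positive, 0.22 to 0.85 | SAP 5.1.1, table |
| Baseline mean, both arms | −2.1 | SAP 2.3 |
| One-year mean, control | 1.1 | SAP 2.3 |
| One-year mean, intervention | −0.5 | SAP 2.3 |
| SD of change | 3.6 | SAP 2.3 |
| Sample size, alpha | 300, 0.05 | SAP 2.3 |

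**1. The plan's own power figure.** Assume 150 per arm and a two-sided test (2.3 does not state sidedness).

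- Standard error = 3.6 × √(2/150) = 0.416
- Difference / standard error = 1.6 / 0.416 = 3.85
- Power ≈ Φ(3.85 − 1.96) = Φ(1.89) = 0.971

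The noncentral t calculation gives 0.970. Splitting the 300 in the recruited ratio of 190:164 gives 0.970 (normal) or 0.969 (t). The stated 97% is reproduced, so 1.6 and 3.6 are the figures the SAP used. A two-sided test does not depend on the sign, so the power is unaffected by this point.

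**2. Is the score really higher = worse?** Yes. Items are coded so that 7 is the most severe, every loading is positive, and dividing by a standard deviation keeps the order. No item is reversed, so the scoring gives no reason to read the sign the other way.

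**3. Direction implied by the premises.** Change > 0 means the one-year score is above the baseline score, which is a worsening. Change < 0 is an improvement.

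**4. The SAP's expected result**

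- Control: 1.1 − (−2.1) = +3.2
- Intervention: −0.5 − (−2.1) = +1.6
- Intervention minus control: 1.6 − 3.2 = −1.6

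| | Implied by definition and scale | As 5.1.1 words it |
|---|---|---|
| Control, +3.2 | worsening | improvement |
| Intervention, +1.6 | smaller worsening | smaller improvement |
| Difference, −1.6 | psyllium better | psyllium worse |

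Only the middle column agrees with 1.2.1 and 2.3.

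**5. Does standardisation alter the between-arm sign?** No. At each visit the same pooled mean is subtracted in both arms, so it cancels in the comparison of arms, and the pooled SD is positive. In one simulated data set with assumed item data (150 per arm, both arms worsening, mean raw item change 0.87 in control and 0.38 in intervention), the mean score change was +1.1 in control and −1.1 in intervention. The arm with less worsening has the lower change score, as in step 4.

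**The case against.** The strongest reply is that the sentence only explains the definition. It is not a computational step, a test or a success criterion. The subtraction, the model, the significance threshold and the power do not depend on it, and the correct direction can be recovered from the scale statement, the item coding, objective 2 and the power section. A careful analyst would probably notice. This stands in part: a reversed conclusion is a possibility, not a certainty, and the p-value and size of the estimate are safe. It does not remove the error. As written, 5.1.1 can be cited for either reading once the results are known, and an SAP should prevent that for a co-primary endpoint.

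A second reply is that 5.1.2 carries over the subtraction and the scoring, but not expressly the sentence on interpretation. That is fair: the reach to the secondary scores is the natural reading, not an explicit statement. As no other direction is given for them, the correction should cover them.

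A third point concerns the scale. Because items are standardised with both arms pooled at each timepoint, the overall mean change is zero with complete data. A positive change then means worsening relative to the other participants, and +3.2 and +1.6 could not both be arm means on that scale. This is correct, but it is a separate matter and leaves the between-arm sign unchanged. It is a good reason to anchor the correction on the treatment coefficient.

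**Conclusion.** The concern holds. The sign rule for the co-primary urgency outcome is the reverse of what the definition and scale in the same section imply, and it contradicts 1.2.1 and 2.3. Nothing else in the SAP corrects it.

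The size is a complete reversal of direction for one of two co-primary outcomes, and by the natural reading of 5.1.2 for all four secondary syndromes. The effect the trial is powered to detect, −1.6 in favour of psyllium, would be described as 1.6 units against it. This figure rests on the means assumed in 2.3; the reversal itself rests only on the subtraction order and the direction of the scale. It must be corrected because it governs how a co-primary result is read, although the analysis itself is untouched.

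**What to change.** Replace the sentence in 5.1.1 with wording such as:

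> A positive change in the urgency score means a worsening and a negative change an improvement. In the regression, a negative treatment coefficient (psyllium minus placebo) favours psyllium.

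Add to 5.1.2 that the same direction applies to the leakage, gas, mucus and blood syndrome scores. All their listed loadings are also positive. If standardisation within each timepoint is kept, add that an individual's change is relative to the other participants at that visit; the statement about the coefficient needs no qualification.

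The cost is one or two sentences, dated before the one-year data are analysed. Data, scoring, model, sample size and power stay as they are, and there is no drawback.
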